## **Risks and Benefits**

The measurement principles of MEG have no harmful effects on subjects. It does not expose the subject to any medication, radiation, or magnetic fields. It non-invasively measures the magnetic fields produced by the human brain.

There is no loud noise generated during acquisition, hence the MEG environment is generally considered as relatively comfortable to subjects, including young children. A possible risk from MEG is the spontaneous boil-off (evaporation) of the liquid helium used for refrigeration of the superconducting sensing system. Although very unlikely, boil-off can occur with minimal risk to subjects. The MEG instrument has safety valves to prevent pressure from building inside the helium reservoir, and if helium is released, the air ventilation inside the MSR has been designed to rapidly exhaust the extremely volatile helium gas out of the MSR. Although helium is inert, there is a risk of oxygen depletion inside the MSR, in case of massive helium boil-off. It would take only seconds for the attending personnel to open the MSR door, which would immediately resolve the situation. Overall, the risk and potential harm from spontaneous helium boil-off in the MEG is minimal and much lower than that from MRI quenching, for instance. This study will include a MEG scan of language and memory testing. There are no known risks of language and memory testing, although some subjects may become frustrated by the tasks or uncomfortable. If this

Title: Pediatric Language and Memory Mapping in Refractory Epilepsy using Magnetoencephalography

PI: [name]

Site: Arkansas Children's Hospital

occurs, breaks will be offered in which subjects may move or change their position until comfortable. The measures of MEG, uses standard clinical tape to stick the coils and EOG/ECG electrodes to the subject's head and chest that may produce mild skin irritation.

Besides the MEG measurements, a structural MRI may be obtained if the subject does not have one with appropriate characteristics for MEG in the medical record. There are also no adverse side effects known for MRI, although some subjects may experience temporary claustrophobia, anxiety, or dizziness. Ferromagnetic artifacts may heat, twist or pull in the MRI. The effect of the strong magnetic fields on fetuses is not well known. Therefore, as is typical with MRI research, subjects with ferromagnetic implants and pregnant women will be excluded from the study. Subjects will be carefully screened and required to complete the ACH's MRI safety questionnaire. If they qualify for scanning, they will change in a gown, and all magnetic parts have to be removed.

Another potential risk to subjects is the potential for loss of confidentiality. Measures to protect the confidentiality of subjects will be implemented as described in the Data Handling and Recordkeeping section below.

The standard-of-care clinical MEG protocol includes the language task, but the [experimental](#) memory task has not been approved by the FDA or ACMEGS [43]. As such, this data will not be utilized in presurgical planning and will be used only for research purposes. Accordingly, there are no guarantees that participation will yield direct benefits to the subjects; however, the knowledge gained from the study could potentially benefit patients in the future. There will be no financial charges to the subject as a result of participation in this study.

## **Adverse Events**

### **Definitions**

**Adverse Event:** An adverse event (AE) is any symptom, sign, illness or experience that develops or worsens in severity during the course of the study. For the purposes of this study, AEs will be collected from the time of consent through the end of the MEG tasks, or following the MRI scan if one is required. Intercurrent illnesses or injuries should be regarded as AEs.

**Serious Adverse Event:** A serious adverse event (SAE) means any untoward medical occurrence with the device: An event is "serious" if it involves considerable detriment or harm to one or more persons (who may or may not be subjects), or required intervention to prevent one or more persons from experiencing considerable detriment or harm. SAEs include:

- Death
- Life-threatening experience - Disease or condition where the likelihood of death is high unless the course of the disease/condition is interrupted or diseases/conditions with potentially fatal outcomes where the end point of the clinical trial analysis is survival
- Inpatient hospitalization or prolongation of hospitalization
- Persistent or significant disability/incapacity
- Congenital anomaly/birth defect in subject's offspring
- Any other important medical event that, based upon appropriate medical judgment, may jeopardize the subject and may require medical or surgical intervention to prevent one of the outcomes listed above. Examples include allergic bronchospasm requiring intensive treatment in an emergency room or at home, blood dyscrasias or convulsions that do not result in inpatient hospitalization, the development of drug dependency or drug abuse, suicidal ideation or attempts, or the unintentional revealing of some genetic information to insurers.

Title: Pediatric Language and Memory Mapping in Refractory Epilepsy using Magnetoencephalography

PI: [name]

Site: Arkansas Children's Hospital

Although an event may be considered “serious” based on previous criteria and should be reported to ORRA immediately, not all SAEs meet IRB or FDA Expedited Reporting criteria.

To avoid confusion, as the terms “serious” and “severe” are not synonymous, the following clarification is given: The term “severe” is often used to describe the intensity (severity) of a specific event (as in mild, moderate or severe myocardial infarction); the event itself; however, may be of relatively minor medical significance (such as a severe headache). This is not the same as “serious”, which is based on subject/event outcome or action usually associated with events that pose a threat to a subject’s life or functioning. Seriousness (not severity) serves as a guide for defining regulatory reporting obligations. [ICH-E2A(II)(B)]

**Unanticipated Adverse Device Effects (UADEs):** A UADE is defined as “any serious adverse effect on health or safety, or any life-threatening problem, or death caused by, or associated with, a device; if that effect, problem, or death was not previously identified in nature, severity, or degree of incidence in the investigational plan, or application (including supplementary application), or any other unanticipated serious problem associated with a device that relates to the rights, safety, or welfare of subjects.” If an unanticipated adverse effect occurs, the investigator will promptly notify the sponsor of such an event within 24 hours of first learning of the event using the FDA MedWatch 3500A form.

**Related:** An event is “related” if more likely than not it was caused by the research activity.

**Unexpected:** An event is “unexpected” when its specificity, nature, severity or incidence is not accurately reflected in the ICF, protocol, or investigator’s Device Manual previously reviewed and approved by the IRB. Examples include a lower rate of response to treatment or a side effect that is more severe than initially expected.

**Study Period:** All AEs will be recorded from the time of consent through the end of the study procedure. All AEs will be captured in the electronic medical record and recorded on the Case Report Forms (CRFs) and AE log.

### ***Monitoring, Recording and Reporting of AEs***

All AEs occurring during the study period as previously defined must be recorded. All relevant historical medical conditions (as determined and documented by Investigator/Clinician that are known/diagnosed prior to the start of the study are to be recorded as medical history. Any medical condition that is present at the time that the subject is screened will be considered as baseline and not reported as an AE. However, if the study subject’s condition deteriorates or exacerbates at any time during the study, it will be recorded as an AE. Pre-existing conditions should be recorded as adverse events only if the frequency, intensity, or the character of the condition worsens during the study.

The clinical course of each event should be followed until resolution, stabilization, or until it has been determined that the study treatment or participation is not the cause. SAEs that are still ongoing at the end of the study period must be followed for up to 30 days to determine the final outcome. Any SAE that occurs after the study period and is considered to be possibly, probably, definitely, or related to the study treatment or study participation should be recorded and reported immediately to the Sponsor.

Title: Pediatric Language and Memory Mapping in Refractory Epilepsy using Magnetoencephalography

PI: [name]

Site: Arkansas Children's Hospital

All subjects will be monitored for AEs during the study. Assessments may include monitoring the subject's clinical symptoms; laboratory, pathological, radiological, or surgical findings; physical examination; or other appropriate tests and procedures.

AE data collection and reporting, which are required as part of every study, are done to ensure the safety of subjects enrolled in the studies and those who will enroll in future protocols. AEs are to be reported in a routine fashion at scheduled times during the trial, such as with the annual continuing review to the IRB. Certain AEs must be reported in an expedited fashion to allow for timely monitoring of subject safety and care.

The reporting of these events depends on the characteristics of the event:

1. Seriousness (grading of event)
2. Relatedness to use of the investigational device or study procedure
3. Expectedness

Steps to Determine if the Event Requires Expedited Reporting:

1. Identify the type of event
2. Grade the event using
3. Determine whether the adverse event is related to the investigational device. Attribution categories are as follows:
  - Unrelated
  - Unlikely
  - Possible
  - Probable
  - Definite
4. Determine expectedness of event. Expected events are those previously identified resulting from administration of the investigational device. An adverse event is considered unexpected when the type or severity of the event is not listed in:
  - Protocol
  - Device Manual
  - ICF

Note: This includes all events that occur within 30 days of the last protocol procedure (2nd IPA procedure). Any event occurring more than 30 days after the last protocol procedure that is possibly, probably, or definitely attributable to the investigational device must be reported according to the instructions above.

### ***Expedited Reporting of AEs***

Only adverse events meeting the UPIRTSO (Unanticipated Problem Involving Risks to Subjects or Others) will need to be reported to the UAMS IRB within the required 10-day allotment of being notified of the event. UPIRTSO requires that an unanticipated problem meet the following qualifications: a) unanticipated or unexpected; b) related to the research; and c) involves new or increased risk to the subject(s). All other adverse events should be recorded and reported to the UAMS IRB at continuing review.

The Sponsor will be promptly notified of all potential SAEs/UADEs by the investigator/study staff using the FDA MedWatch 3500A. The Sponsor will evaluate all potential SAEs/UADEs and report these evaluations in accordance with 21 CFR 812. All other SAEs/UADEs not expeditiously reported will be reported to the Sponsor and IRB in the Annual Progress Report (APR).

Title: Pediatric Language and Memory Mapping in Refractory Epilepsy using Magnetoencephalography  
PI: [name]  
Site: Arkansas Children's Hospital

Report all deaths to the Sponsor (ORRA) as soon as possible, preferably within 24 hours, but no later than 48 hours, of learning of the subject's death, regardless of whether it is related or unrelated to the investigational device. A death due to a terminal condition of the research subject would be considered anticipated and not related to the research.

The Sponsor will report deaths in accordance with 21 CFR 812.

## **Clinical Site Monitoring**

Clinical site monitoring will be conducted by the UAMS Office of Research Regulatory Affairs (ORRA) to ensure that the rights and well-being of human subjects are protected, that the reported trial data are accurate, complete, and verifiable from source documents, and that the conduct of the trial is in compliance with the currently approved protocol/amendment(s), ICH GCP, and applicable regulatory requirements.

Monitoring specialists from ORRA will conduct periodic on-site, comprehensive monitoring as determined by a protocol specific monitoring plan, which will be provided by the ORRA Monitoring Unit to the Investigator.

## **Deviations and Violations**

*Protocol Deviation:* A deviation is any unintentional change, divergence, or departure from the study design or procedures defined in the protocol. Protocol deviations will be tracked and compiled in a Protocol Deviation Log. Deviations that potentially cause concern for the subject health, safety, or rights will be reported to the Sponsor as soon as possible for guidance on reporting.

*Protocol Violation:* A violation is a change to, or non-compliance with, the IRB-approved procedures without prior Sponsor and IRB approval (excluding changes made to eliminate apparent immediate hazard to subjects). A violation may affect health, safety, or rights of a subject. Any violation will be reported immediately to the Sponsor for guidance on reporting.

If the protocol deviation/protocol violation does not represent a significant alteration in the approved protocol and/or affect the safety or welfare of the subject, it will be reported to the UAMS IRB at the time of Continuing Review. If the protocol deviation/violation represents a significant alteration in the approved protocol and/or if it affects the safety or welfare of the subject, it must be reported to the Sponsor and UAMS IRB immediately.

## **Data Handling and Recordkeeping**

The Principal Investigator will carefully monitor study procedures to protect the safety of research subjects, the quality of the data, and the integrity of the study. All study subject material will be assigned a unique identifying code or number. The key to the code will be kept in a password-protected file on a secure, password-protected computer in the principal investigator's office. Only the Principal Investigator (PI) will have access to the code and information that identifies the subject in this study. Clinical data and medical evaluation information will be obtained from the ACH Electronic Medical Record.

Title: Pediatric Language and Memory Mapping in Refractory Epilepsy using Magnetoencephalography

PI: [name]

Site: Arkansas Children's Hospital

- Medical record information to be collected will include the subject's name, address, telephone number, age, sex, race, ethnicity, head circumference, education, medical history - especially related to epilepsy such as epilepsy duration, results of routine EEG and imaging tests.

At the conclusion of the study, the secure file containing linkages between the study ID and any subject identifiers (e.g., MRN, DOB) will be deleted, while the data will be stored for no more than 10 years or until the last subject reaches the 23rd birthday. If consent was granted by the subject for future research then their data will be retained for an unspecified amount of time for use in future research which will be limited to future IRB-approved studies evaluating brain activity. All stored data will be de-identified. Data will be stored in the ACH MEG Center and only study personnel authorized to view the data will have access. Subjects may request to withdraw from the study by calling the PI at the number listed in the ICF or withdraw their data for future research use by writing a letter to the PI at the address specified in the HIPAA Authorization of the ICF.

## **Data Analysis**

### ***Preprocessing***

MEG data will be exported for further analysis from the acquisition computer to the signal processing research software, Brainstorm [66] (<https://neuroimage.usc.edu/brainstorm/>), which is an open-source application dedicated to the analysis of brain recordings. Next, data will band-pass filtered between 0.5Hz to 100Hz and a notch filter will be applied for power-line noise removal (60Hz, 2nd order IIR notch filter with zero-phase lag). We will perform visual inspection to mark bad channels and segments. Data will be preprocessed for eye-blink and electrocardiogram reduction using a signal-space projection (SSP) technique [67]. The corresponding triggers recorded during acquisition will be used to import MEG epochs in the time window ranging from -200s to +800s with respect to the trigger [68, 69]. Baseline correction will be applied on the 200s before the trigger. Next, we will average across epochs to obtain an ERF waveform per subject for the language and memory tasks. Resting state data will use for baseline source imaging.

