fMRI is the most widely used of the minimally/non-invasive techniques for presurgical language mapping in children [11]. However, MEG is gaining increasing acceptance as a non-invasive method as an adjunctive part of the pre-surgical functional mapping procedure [12]. Especially for language identification in pediatric cases, the quiet environment of the MEG room and the head-motion-tracking methods available in recent MEG systems, increase the likelihood of success with language lateralization in young populations. Further, MEG allows examining both hemispheres simultaneously, which is especially useful in epileptic populations, in which language lateralization is more variable. MEG language localization studies have shown encouraging results with a wide variety of paradigms, especially in localization of receptive language areas that are well documented [13, 14] and validated [15, 16]. The suitability of MEG language lateralization protocols in adults as an alternative to the Wada procedure have been addressed with validation studies conducted using various methodologies and exhibit overall high concordance rates (about 86-92%) [17-20]. Language lateralization is calculated in both hemispheres by localizing dipole sources (equivalent current dipole, ECD model) accounting for late auditory evoked field (AEF) components (150-700 ms after stimulus onset). These late components localize to language-related areas (mainly within posterior temporal areas) of the brain regardless of the modality of stimulus presentation [21]. Depending on the activation task, the dipole sources can be used to identify the location of receptive (Wernicke's area) or expressive language-specific (Broca's area) cortex. The degree of hemispheric asymmetry in the duration or strength of activation can also be calculated as an index of hemispheric dominance for language functions. Estimations of language lateralization with MEG [22] have mainly been based on recognition memory tasks for spoken words [23] or by listening to synthesized vowel sounds [24]. Thus, most of the MEG language studies have focused on receptive language areas. However, other reports exist on frontal circuits in expressive language [25-27] and basal temporal areas during semantic language tasks (verb generation) [28, 29]. Recent MEG language studies have reported the feasibility of passive paradigms in children and adolescents under sedation [30] and during sleep [31]. A recent MEG study [32] uses a verbal memory and verbal fluency tasks showing activation of the left hippocampus and in Wernicke's area in favor of the left hemisphere. Authors found higher concordance rates between a verbal memory paradigm and language dominance in controls (using handedness as criterion) and in subjects with epilepsy (using fMRI or Wada as criterion), compared with a verbal fluency task. Only the concordance for verbal memory reached statistical significance, with 93% agreement. Previous studies in pediatric epilepsy have shown atypical language lateralization [33] and that the word recognition task is the only language comprehension task used in both children and adults that yields high concordance between MEG and the Wada test for language lateralization [22]. Despite all contributions of MEG in the assessment of language localization in typically developing individuals, studies in pediatric populations with epilepsy is still relatively small especially in single subjects, which is necessary for clinical utility.

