### ***Inclusion Criteria***

- 8 to 21 years old
- Drug-resistant focal epilepsy
- Enrolled in the Arkansas Children's Neuroscience Center Comprehensive Epilepsy Program
- Under evaluation for resective surgery
- English speakers. This is not a treatment/intervention study.

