## **MEG Acquisition**

Each subject will have one MEG session with the recordings of baseline resting state, language and memory protocols. Subjects will have a break period between the language and memory tasks. MEG recordings will be acquired for approximately 35 minutes. The subject will be allowed to practice the language and memory tasks before the MEG recording to feel familiar with them. This practice phase will be a short version of the task administered by a computer and will take approximately 6 minutes.

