## ***MEG System Equipment***

Arkansas Children's Hospital (ACH) hosts the only one of its kind in the state and latest-generation whole-head MEG system (TRIUX™ neo, see Fig. 1A) with helium recycling technology for zero helium boil-off. MEG system is a clinical device with Food and Drug Administration (FDA) approval. The MEG system consists of 306 (see Fig. 1C) Superconducting Quantum Interference Devices (SQUIDs). The MEG scan is located inside of a magnetically shielded room (MSR, see Fig. 1D) to reduce environmental noise to a level compatible with the brain signals. The MEG system is equipped with a specially designed bed (Fig. 1A) and chair (Fig. 1B) for supine and seated measurements (reclined and upright). MEG laboratory is equipped with an audio-video surveillance and communication system, and additional electronics to design specific protocols to record MEG in response to external stimuli. Because exact information about the relative position of the head with respect to the sensor array is necessary for post-analysis, MEG laboratory is equipped with "head position indicator" coils and digitization system to determinate this relative position. The 3-dimensional (3D) digitization system is used in the preparation phase before MEG measurements to digitize the positions of the coils as well as the landmarks on the head. The locations of the landmarks are used to establishing a coordinate transformation between MEG and the anatomical information.

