### **Resting State Measure**

Baseline brain activities will be measured for 5 minutes. The subject will be asked to remain still with eyes closed and rest.

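### Head position coils are fitted, but the plan does not say when head position is measured or how head movement is corrected or excluded before the left-right difference is computed

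*Combined protocol and SAP*

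**What the plan says.** **Head position.** MEG System Equipment justifies the HPI coils and the digitiser by saying that "exact information about the relative position of the head with respect to the sensor array is necessary for post-analysis". MEG Preparation Phase attaches five coils and digitises them with the anatomical landmarks before the subject goes under the helmet. Background and Rationale adds that "the head-motion-tracking methods available in recent MEG systems, increase the likelihood of success with language lateralization in young populations".

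**The session.** The age range is "8 to 21 years old", and sedation during MEG is an exclusion criterion. MEG Acquisition states that "MEG recordings will be acquired for approximately 35 minutes" and that "Subjects will have a break period between the language and memory tasks". Under Risks and Benefits, if a subject becomes frustrated or uncomfortable, "breaks will be offered in which subjects may move or change their position until comfortable". A request to keep still is written only for the 5-minute resting recording: "The subject will be asked to remain still with eyes closed and rest".

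**Processing.** Preprocessing lists a 0.5-100 Hz band-pass filter, a 60 Hz notch filter, visual marking of bad channels and segments, then "Data will be preprocessed for eye-blink and electrocardiogram reduction using a signal-space projection (SSP) technique", followed by epoching, baseline correction and averaging. Source Imaging adds an empty-room noise covariance, the forward model, sLORETA and an amplitude cut-off of 3.2 nAm.

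**Outcome.** Statistical Analysis defines hemispheric dominance as the difference in activation between the two sides, compares left with right at group level at alpha 0.05, and expects the pilot to inform the size of later studies.

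**The concern.** The plan recognises that head position matters and fits the hardware to measure it. The written analysis then never uses it. If the head lies nearer one side of the helmet than the source model assumes, signal rises on that side and falls on the other. That error has the same form as the quantity being estimated, a left-right difference.

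Two things are at stake. The first is the individual dominance estimate, since the Background says that single-subject mapping is what clinical use requires. The second is the between-subject SD, which would carry movement error into the sizing of later studies. The fixed amplitude cut-off could add to the problem if sources on the attenuated side fall below it and are dropped.

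**Working it through.** **1. Text check.** The documents give no movement figure, so there is none to reproduce. I compared each thing a head-movement plan needs with the text.

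| Element | In the documents? |
|---|---|
| Coils fitted and digitised | Yes, before the recordings |
| When head-to-sensor position is read (once, per run, continuously) | Not stated |
| Re-measurement after a break | Not stated |
| Movement compensation, or alignment of runs to one position | Not stated |
| Displacement limit or exclusion rule | Not stated |

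Digitisation does not fill the gap. It is done outside the shielded room and places the coils relative to the landmarks. It cannot show where the head later sits under the helmet. The steps that are listed do not fill it either. Filters and SSP do not correct displacement, and visual marking has no displacement criterion, although it may remove gross movement artefact.

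**2. Opportunity for movement.** The language task has 3 blocks of 5 + 40 = 45 words, so 135 words. With 2.5 to 3.5 s per word on average, depending on how the interval is counted, it lasts about 5.6 to 7.9 minutes. The memory task is stated as around 16 minutes. With 5 minutes of rest, recording comes to about 27 to 29 minutes. The stated 35 minutes is plausible once breaks or set-up are counted. The memory task is therefore long enough for drift, and an unscheduled break during a task could put two head positions into one average.

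**3. Size for one subject (illustration).** My assumptions are two equal, symmetric sources, each at distance d from its nearest sensor; sensor amplitude falling as 1/d²; a sideways shift s lasting through the whole average; and a model left at the starting position. The index is (L-R)/(L+R).

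- Ratio = ((d+s)/(d-s))²; false index = (ratio - 1)/(ratio + 1).
- d = 40 mm, s = 5 mm: (45/35)² = 1.65, index 0.246.
- d = 50 mm, s = 5 mm: (55/45)² = 1.49, index 0.198.
- d = 60 mm, s = 5 mm: (65/55)² = 1.40, index 0.166.

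Over d = 40 to 60 mm, the false index is 0.07-0.10 for 2 mm, 0.17-0.25 for 5 mm and 0.32-0.47 for 10 mm. With 1/d³ fall-off, the 5 mm range becomes 0.25-0.36.

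**4. Effect on the SD (illustration).** Assume a between-subject SD of 0.30 without movement error, and a false index of fixed size b and random sign.

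- b = 0.08: SD = √(0.30² + 0.08²) = √0.0964 = 0.31; variance ratio 0.0964/0.09 = 1.07.
- b = 0.20: SD = √(0.30² + 0.20²) = √0.13 = 0.36; variance ratio 0.13/0.09 = 1.44.

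For a fixed target difference, sample size scales with the variance. A later study that did control movement would therefore be planned about 7% to 44% too large.

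**5. Group comparison, only if every shift went the same way.** For a two-sided one-sample t test at 0.05 with SD 0.30, the noncentrality is b√n/SD. With n = 10 it is 0.84 for b = 0.08 and 2.11 for b = 0.20, giving rejection rates of 12% and 47% with no true asymmetry. With n = 15 it is 1.03 and 2.58, giving 16% and 67%. Both sample sizes are shown because Study Design and Procedures says ten subjects and Study Population says fifteen.

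**The case against.** The other side has several good points.

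- **Silence is not proof of a single measurement.** A reader might infer that head position is read once and that all epochs are modelled from it. The documents do not say so. If position is read at the start of each run, a shift during a break enters that run's forward model and only within-run movement remains. This stands, and it limits the point to what is unstated.
- **Movement is allowed in breaks, not while recording.** A reader might infer that subjects may shift about throughout the 35 minutes. The wording concerns breaks offered for discomfort, and the 35 minutes is recording time. The scheduled break falls between tasks. If each task has its own average, which is the natural reading, that break does not mix positions within an average. This stands; drift and unscheduled breaks remain.
- **The language task follows a professional society's standard protocols**, which may cover head position and cannot be seen here. This stands in part. Risks and Benefits says that society has not approved the memory task, so the same cover cannot be assumed there.
- **The arithmetic is a nearest-sensor model on assumed inputs.** The plan uses sLORETA estimates from a 306-sensor system, and (L-R)/(L+R) is not its stated index. This stands: the figures show direction and rough scale only.
- **A biased group result does not follow.** Shifts in random directions mainly add noise, and nothing in the documents suggests a common direction. No outcome is labelled as the main one, and Aim 1 is feasibility. This stands.

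**Conclusion.** The point holds as a gap in the stated processing. The plan provides the means to measure head position and calls exact position necessary. It does not say when position is measured, and no step corrects or excludes movement before averaging and the hemispheric comparison. In unsedated subjects aged 8 to 21, this can distort an individual's dominance estimate and inflate the SD passed to future sample-size work.

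The size is unknown because the documents contain no movement data. The illustrative range is a false sensor-level index of 0.17 to 0.25 for a lasting 5 mm sideways shift, less if only some epochs are affected. The illustrative SD of 0.30 rises to between 0.31 and 0.36. These figures rest on the assumed distances, fall-off and baseline SD, and on the shift not being modelled.

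The documents do not support the stronger reading that the group left-right comparison is biased; the rejection rates in step 5 apply only with shifts in a common direction. This is a cheap improvement, not a flaw that invalidates the pilot.

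**What to change.** **MEG Acquisition:** state that head position is recorded continuously with the coils already fitted, or at least re-measured at the start of every run and after every break.

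**Preprocessing:** before averaging, apply movement compensation and align each subject's runs to one head position. Exclude segments beyond a displacement limit that the investigators set in advance.

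**Reporting:** give displacement per subject and task as a feasibility result under Aim 1. This would also supply the movement figure that the documents now lack.

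**Cost:** a small change to acquisition, one added processing step, and some epochs lost in subjects who move. No new equipment is needed for the measurement itself.
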